6. INVESTIGATIONAL PLAN

6.1 VISIT SCHEDULE

Written informed consent must be obtained before any protocol specific screening assessments are performed, and may be obtained prior to the screening visit. Separate written informed consents must be obtained before the collection of samples for pharmacogenetic and biomarker analyses.

Eligible patients will receive the randomised study medication for unlimited number of weeks, until any of the criteria for stopping medication are met (see [Section 3.3.4](#)). During the treatment phase, visits should be performed weekly, but within two days of the scheduled date. The scheduled time interval for each visit is relative to the date of randomization. Following the permanent discontinuation of study medication (EOT visit) and the follow-up visit, patients will be followed until death by contacts every four weeks.

In case a patient missed a visit and the patient reports to the investigator between the missed visit and the next scheduled visit, the date of the report and the reason for the delayed visit should be noted in the patient's chart. The next visit, however, should take place at the scheduled time. In the event of any interruption/delay of treatment, the tumour assessment schedule should not be changed.

6.2 DETAILS OF TRIAL PROCEDURES AT SELECTED VISITS

The assessments to be performed at the respective visits are outlined in the [Flow Chart](#) and the procedures for each assessment are described in [Section 5](#).

6.2.1 Screening and randomization

The screening visit should be performed within 14 days before the first administration of study medication. Patients who meet the eligibility criteria will be randomised and treatment should commence on the same day the patient is randomised, but at least within four calendar days after randomization.

Baseline tumour images, obtained maximum 21 days prior to start of treatment, are acceptable if the same technique can be used for the following visits and the images fulfil the central imaging review requirements. If the screening images were obtained for routine assessment before informed consent, a clarification that the imaging was not performed for the purpose of the present trial must be clearly documented on source note.

If a patient is screened and screening images do not show progression after platinum based therapy, patient can be kept in screening until new images are obtained that can confirm PD according to RECIST. Visit 1 procedures must be repeated after PD is confirmed to ensure eligibility criteria are fulfilled before randomization.

HRQOL questionnaires should be filled in by the patient as the first activity at the relevant visits prior to receiving any new information about their disease status in order to avoid bias.

6.2.2 Treatment period

Patients randomised to Afatinib will receive continuous daily oral treatment.

A Patient Diary will be dispensed to patients randomised to Afatinib to record study medication. Whenever dispensing a new Afatinib bottle, a new diary should be dispensed and the completed diary should be collected from the patient. In case a patient is illiterate, site should aim to train the patient's relative or care-giver how to complete the Patient Diary, if at all possible.

Patients randomised to methotrexate will receive weekly bolus injections.

The treatment period will continue for unlimited number of weeks, until disease progression is confirmed by tumour imaging or any of the other criteria for stopping medication are met (see [Section 3.3.4](#)).

There will be weekly visits during the treatment period, and for the first 24 weeks of treatment, the Flow Chart entitled "[Visits 1-26](#)" should be adhered to. Patients continuing beyond 24 weeks should then be followed according to the Flow Chart entitled "[Visit 27 and onwards](#)".

Tumour imaging

Tumour imaging will be performed every 6 weeks during the first 24 weeks of treatment, and hereafter every 8 weeks until disease progression or start of subsequent anti-cancer therapy. As the primary endpoint of the trial is based on the tumour imaging evaluation, it is important that the imaging schedule is held. After the database lock for primary analysis, the imaging intervals can change to follow local site standard (if no standard; every 16 weeks).

Health related quality of life

To avoid potential bias, HRQOL questionnaires should be filled in by the patient as the first activity when the patient comes to the clinic prior to seeing the clinician and prior to receiving any new information about their disease state. After database lock for primary analysis, the completion of the questionnaires is no longer required at any visit.

Biomarkers and pharmacogenetics

The tumour tissue slides and core punch biopsies should be sent to the central laboratory as soon as possible as described in the investigator lab manual. The serum sample should be drawn at Visit 2 (see [Flow Chart](#)) and sent to the central laboratory as described in the investigator lab manual.

For patients consenting to the pharmacogenetic part of the trial, blood sampling should be performed, preferably at Visit 2, and sent to the central laboratory.

6.2.3 End of treatment and follow-up period

6.2.3.1 End of treatment visit

The end of treatment (EOT) visit will be performed when the patient permanently discontinues the study medication.

The decision to permanently discontinue study medication due to disease progression must be based on the evaluation of tumour imaging. If the decision to permanently discontinue the study medication is taken during a scheduled visit, the EOT visit procedures should be performed instead of the scheduled visit. If the decision is taken between scheduled visits, the EOT visit should be performed no later than seven days after the last treatment administration.

In the case study medication is permanently discontinued due to reasons other than disease progression or withdrawal of consent, the EOT visit will be performed, and the patient should continue the tumour imaging according to the pre-defined schedule until disease progression or start of other anti-cancer therapy. If a patient who did not have disease progression needs commence of other anti-cancer therapy, tumour imaging should be performed close to the start of new anti-other therapy. After the database lock for primary, the requirement to continue imaging for patients who permanently discontinued study medication due to other reasons than disease progression will be removed.

The investigator will, in consultation with the patient, decide the future treatment.

The patients that are still on treatment at one year after last patient randomized can continue drug administration from the trial, until disease progression or earlier if stop of treatment for other reasons is considered the best interest for the patient per investigator's judgment. An interim database lock will occur at around one year after last patient randomized. After this interim lock, only AE, dose change, drug termination date and cause of termination are required to be collected in RDC or BRAVE, and all the other trial procedures will be waived.

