| Weeks after randomization | 176 (+/-2) | 183 (+/-2) | 190 (+/-2) | 197 (+/-2) | 204 (+/-2) | 211 (+/-2) | 218 (+/-2) | 225 (+/-2) | Repeat visits 27 to 34 | 0-7 after last dose | +28 (+7) after EOT | Every 4 weeks (+/-7 days) |
| Body weight | X | X | X | X | X | X | X | | | X | | |
| Vital signs | X | X | X | X | X | X | X | | | X | X | |
| Physical, skin and H&N exam ² | | | | X | | | | X | | X | X | |
| Tumour imaging ³ | | | | | | | | X | | X ⁴ | X ⁴ | X ⁴ |
| ECOG Performance status | | | | X | | | | X | | X | X | |
| 12 Lead ECG | | | | | | | | X ⁵ | | X ⁶ | | |
| HRQOL ⁷ | | | | | | | | X | | X | X | |
| Health care resource use/Home care | | | | X | | | | X | | | | |
| Dispense Afatinib | every 4 weeks | | | | | | | | | | | |
| Afatinib treatment ^{8,14} | Continuous | | | | | | | | | | | |
| Compliance check (Afatinib) | when dispensing new study medication | | | | | | | | X | | | |
| Methotrexate treatment | X | X | X | X | X | X | X | X | | | | |
| Termination of study medication | | | | | | | | | | X | | |
| Adverse events | X | X | X | X | X | X | X | X | X | X | X ⁹ | X |
| Concomitant therapy | X | X | X | X | X | X | X | X | | X | X | X ¹⁰ |
| Safety laboratory testing ¹¹ | | | | X | | | | X | | X | X | |
| Pregnancy testing ¹² | | | | | | | | | | X | | |
| Vital status ¹³ | | | | | | | | | | | | X |

Treatment period Patients may continue on treatment for unlimited visits, until the criteria for stopping medication are met (see [Section 3.3.4](#)).

Visits 27-34 are repeated when a patient continues beyond Visit 34.

EOT

End of treatment; EOT visit is done within 7 days after last drug administration.

If a patient permanently discontinues study treatment at a scheduled visit, the EOT visit should be performed instead of this visit.

FUV

Follow-up visit; all patients should have a follow-up visit 28 days (+7days) after the EOT visit.

OP

Observational Period; All patients will be followed-up for overall survival at 4 week intervals after the last follow-up for progression visit until death, withdraw of consent, lost to follow-up or completion of the whole trial whatever occurs earlier. See [section 5.2.2.2](#). After database lock for primary analysis, frequency will be every 3 months until one year after last patient randomized.

Proprietary confidential information. © 2019 Boehringer Ingelheim International GmbH or one or more of its affiliated companies

- 1) Recommended day for visit.

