- 13) All patients will be followed-up for overall survival at 4 week intervals after the last follow-up for progression visit until death, withdraw of consent, lost to follow-up or completion of the whole trial whatever occurs earlier. See [section 5.2.2.2](#). Observational contacts may be performed by telephone interview if patients are unable to visit the investigator. Deaths must be recorded in the eCRF within 48 hours of a site becoming aware of a patient death. After database lock for primary analysis, these Observational contacts will be at 3 month intervals until one year after last patient randomized.
- 14) The patients that are still on treatment at one year after last patient randomized can continue drug administration from the trial, until disease progression or earlier if stop of treatment for other reasons is considered the best interest for the patient per investigator's judgment. An interim database lock will occur at around one year after last patient randomized. After this interim lock, only AE, dose change, drug termination date and cause of termination are required to be collected in RDC or BRAVE, and all the other trial procedures will be waived.

TABLE OF CONTENTS

| | |
|--|-----------|
| TITLE PAGE | 1 |
| CLINICAL TRIAL PROTOCOL SYNOPSIS | 2 |
| FLOW CHART | 5 |
| TABLE OF CONTENTS | 10 |
| ABBREVIATIONS | 15 |
| 1. INTRODUCTION..... | 17 |
| 1.1 MEDICAL BACKGROUND | 17 |
| 1.1.1 Head and neck squamous cell carcinoma | 17 |
| 1.1.2 Treatment of incurable HNSCC | 17 |
| 1.2 DRUG PROFILE | 18 |
| 1.2.1 Afatinib..... | 18 |
| 1.2.2 Preclinical data | 19 |
| 1.2.3 Previous clinical experience..... | 19 |
| 2. RATIONALE, OBJECTIVES, AND BENEFIT - RISK ASSESSMENT | 22 |
| 2.1 RATIONALE FOR PERFORMING THE TRIAL | 22 |
| 2.2 TRIAL OBJECTIVES..... | 22 |
| 2.3 BENEFIT – RISK ASSESSMENT | 23 |
| 3. DESCRIPTION OF DESIGN AND TRIAL POPULATION..... | 25 |
| 3.1 OVERALL TRIAL DESIGN AND PLAN..... | 25 |
| 3.1.1 Administrative structure of the trial | 27 |
| 3.2 DISCUSSION OF TRIAL DESIGN, INCLUDING THE CHOICE OF CONTROL GROUP | 28 |
| 3.3 SELECTION OF TRIAL POPULATION..... | 28 |
| 3.3.1 Main diagnosis for trial entry | 29 |
| 3.3.2 Inclusion criteria | 29 |
| 3.3.3 Exclusion criteria..... | 30 |
| 3.3.4 Removal of patients from this trial or assessments..... | 31 |
| 3.3.4.1 Removal of individual patients | 31 |
| 3.3.4.2 Discontinuation of the trial by the sponsor | 32 |
| 4. TREATMENTS..... | 34 |
| 4.1 TREATMENTS TO BE ADMINISTERED | 34 |

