Based on the experience from previous Afatinib studies, a continuous oral daily dose of 40 mg Afatinib, together with proactive management of common side effects and the proposed dose reduction scheme, is expected to be well tolerated. If no or minimal AE is observed in the first four weeks of treatment, the dose of Afatinib could be escalated to 50 mg. This will give the patients an opportunity to receive the highest dose of Afatinib based on their tolerability.

Methotrexate is chosen as the comparator in this trial because it has been approved in EU and the US as the second-line chemotherapy for HNSCC ([R10-5909](#), [R10-5936](#)). Its most common side effects are stomatitis, leukopenia and nausea. Similar to all other cytotoxic agents, these side effects are not always reversible, which could lead to less adherence to treatment and/or early interruption of treatment.

Although rare, a potential of drug-induced liver injury (DILI) is under constant surveillance by sponsors and regulators. Therefore, this trial requires timely detection, evaluation, and follow-up of laboratory alterations of selected liver laboratory parameters to ensure patients' safety.

In the present trial, there will be regular and frequent assessment of clinical benefit (including early imaging with first radiological tumour assessment after 6 weeks of treatment). All patients will have weekly visits to ensure close monitoring of AEs. An independent data monitoring committee (DMC) will oversee the trial and will advise on the further trial conduction based on the ongoing assessment of efficacy and safety data (see [Section 3.1.1](#)).

In conclusion, the risk benefit assessment for Afatinib and methotrexate in the treatment of R/M HNSCC in the proposed setting is positive. The potential benefits for trial patients on either treatment arm outweigh treatment-associated risks.

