The dose of Afatinib must be escalated to 50 mg (at the earliest after 28 days on study medication) if all the following criteria are met:

- CTCAE grade ≤ 1 skin rash (any aetiology/relation)
- Absence of diarrhoea, mucositis, and/or any drug-related event (any grade) other than skin rash CTCAE grade 1 and
- Compliance of Afatinib intake is in 80~100% as described in [Section 4.3](#)
- Dose was not previously reduced due to any of the AEs depicted in the dose reduction scheme (see [Table 4.1.4.1: 1](#))

Dose escalation is prohibited in any situation other than that described above. The patient should remain on 50 mg unless dose reduction becomes necessary (see Table 4.1.4.1: 1).

Dose reduction, Afatinib

Treatment related AEs will be managed by treatment interruptions and subsequent dose reductions of Afatinib according to the schedule described in Table 4.1.4.1: 1. Dose reductions

Proprietary confidential information. © 2019 Boehringer Ingelheim International GmbH or one or more of its affiliated companies

will apply to individual patients only. Once the dose has been reduced, it may not be increased later.

Table 4.1.4.1: 1 Afatinib dose reduction scheme

| AE type and CTCAE grade |
|--|
| Events related to study medication; 
• Any drug related AE grade ≥ 3.• Diarrhoea grade ≥ 2 persisting for 2 or more consecutive days (≥ 48 hours) despite adequate anti-diarrhoeal medication/hydration.• Nausea and/or vomiting grade ≥ 2 persisting for 3 or more consecutive days despite anti-emetic treatment/hydration.• Reduced renal function to grade ≥ 1 as measured by serum creatinine, proteinuria, or glomerular filtration rate. |
| Action |
| Interrupt Afatinib treatment until patient has recovered to grade ≤ 1 (note for reduced renal function, recovered to grade <1) or to the CTCAE grade present at baseline ¹ . If patient has not recovered within 14 days, study medication should be permanently discontinued ² . |
| Dose reduction scheme |
| Resume treatment at reduced dose according to; 
• 40 mg if the dose prior to the interruption was 50 mg.• 30 mg if the dose prior to the interruption was 40 mg.• 20 mg if the dose prior to the interruption was 30 mg. No dose reduction is allowed below 20 mg. |

1 Baseline is defined as the CTCAE grade prior to start of treatment

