5.2.2.1.7 Protocol Defined Adverse Event of Special Interest [AESI]

Although rare, drug-induced liver injury (DILI) is under constant surveillance by sponsors and regulators and is considered a protocol-defined adverse event of special interest (AESI). Timely detection, evaluation, and follow-up of laboratory alterations of selected liver laboratory parameters to distinguish an effect of the underlying malignancy on liver function from other causes are important for patient safety. The following are considered as AESI:

- For patients with normal liver function (ALT, AST, bilirubin within normal limits) at baseline an elevation of AST and/or ALT ≥ 3 fold ULN combined with an elevation of bilirubin ≥ 2 fold ULN measured in the same blood draw sample and/or marked peak aminotransferase (ALT, and/or AST) elevations ≥ 10 fold ULN.
- For patients with abnormal liver function at baseline an elevation of AST and/or ALT ≥ 5 fold ULN combined with an elevation of bilirubin ≥ 2 fold ULN measured in the same blood draw sample and/or marked peak aminotransferase (ALT, and/or AST) elevations ≥ 10 fold ULN.

Patients showing these lab abnormalities need to be followed up according to [Appendix 5](#) of this clinical trial protocol and the “DILI checklist” provided in the ISF.

Protocol-defined AESIs are to be reported in an expedited manner similar to SAEs, even if they do not meet any of the seriousness criteria – for details see [Section 5.2.2.2](#).

If the investigator determines any protocol-defined AESI is related to study drug, the administration of the study drug must be managed according to [Section 4.1.4](#) of the protocol.

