5.2.3 Assessment of safety laboratory parameters

Blood and urine samples will be collected at the time points specified in the [Flow Chart](#) and analysed in a laboratory facility at (or close to) the investigational site. The sampling details are recorded in the eCRF. The laboratory report should be reviewed, signed and dated by the investigator.

Safety laboratory assessments may be performed according to local practice but must include at least the following parameters:

| | |
|--------------|--|
| Haematology | Red blood cell count (RBC), haemoglobin, haematocrit, white blood cell count (WBC) and differential, platelet count, reticulocyte number. |
| Biochemistry | Serum glucose, sodium, potassium, calcium (including ionized calcium), magnesium, creatinine, urea, aspartate amino transferase (AST), alanine amino transferase (ALT), alkaline phosphatase, lactate dehydrogenase, |

Proprietary confidential information. © 2019 Boehringer Ingelheim International GmbH or one or more of its affiliated companies

total bilirubin, γ -glutamyltransferase (GGT), albumin, creatine phosphokinase (CPK).

In case CPK is higher than ULN, further evaluation (e.g., by Troponin I assays, CPK isoenzymes and ECG exam) should be performed.

Glomerular Filtration Rate (GFR) will be estimated by the Cockcroft-Gault Formula utilising serum creatinine values (see [Appendix 2](#)).

Coagulation Prothrombin time (PT), partial thromboplastin time (PTT).

Urinalysis pH, glucose, erythrocytes, leukocytes, protein, nitrite will be analysed at baseline and EOT only. In case of values out of range, further evaluation should be performed.

Pregnancy test β -HCG testing in serum (alternatively in urine) will be performed in women of childbearing potential.

In case there is an obvious reason (for instance dehydration) for the laboratory results being abnormal at the screening visit, the laboratory sample(s) may be repeated.

The screening laboratory sampling must be done within two weeks before randomization. If the randomization is delayed beyond this, then the screening laboratory sampling must be repeated.

In case of neutropenia CTCAE grade 4, blood will be examined as clinically indicated at the discretion of the investigator until recovery.

Local lab results will be collected in the eCRF. Any AEs detected will be reported, see [Section 5.2.2.1.6](#).

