10.4.2 Procedures

Investigator must pay attention to results of ALT/AST/bilirubin tests. Any elevation of ALT/AST and bilirubin qualifying as laboratory alert in Section 5.2.2.1.7 would be confirmed by local laboratory on initial sample. If due to technical error, the laboratory is not able to complete the confirmatory testing, an alert will be generated if possible.

If a site receives a potential DILI alert notice from the local laboratory or if the investigator notices the elevated ALT/AST/bilirubin reach the level in Section 5.2.2.1.7, the following must be completed:

- Evaluate patient within 48 hours AND
- Perform the following laboratory tests locally for confirmation:
 1. Repeat of AST, ALT, bilirubin (with fractionation to total and direct)
 2. Haptoglobin
 3. Complete blood count and cell morphology
 4. Reticulocyte count

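### After the interim lock, patients may stay on trial-supplied afatinib with no required periodic blood test, although the renal interruption rule and the laboratory-defined liver event still apply

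*Protocol*

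**What the plan says.** Protocol Section 6.2.3.1 and footnote 14 of the Flow Chart for Visit 27 onwards carry the same text. Patients still on treatment one year after the last randomisation "can continue drug administration from the trial, until disease progression or earlier if stop of treatment for other reasons" are in their best interest. After the interim lock, adverse events and dose changes are kept, and for the rest "drug termination date and cause of termination are required to be collected in RDC or BRAVE, and all the other trial procedures will be waived". No exception is listed.

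The laboratory schedule has a single source. Section 5.2.3 states "Blood and urine samples will be collected at the time points specified in the" Flow Chart. From week 25, the row "Safety laboratory testing" is marked at Visits 30 and 34 (weeks 28 and 32, then repeating, so every four weeks), at end of treatment (EOT) and at the follow-up visit (FUV).

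Three provisions that rely on laboratory values have no time limit:

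- Table 4.1.4.1: 1 requires afatinib to be interrupted, then reduced, when renal function falls to grade 1 or worse, "as measured by serum creatinine, proteinuria, or glomerular filtration rate".
- Section 5.2.2.1.7 defines the liver adverse event of special interest by AST or ALT together with bilirubin "measured in the same blood draw sample and/or marked peak aminotransferase (ALT, and/or AST) elevations" of at least ten times the upper limit of normal.
- Section 2.3 says that "this trial requires timely detection, evaluation, and follow-up of laboratory alterations of selected liver laboratory parameters".

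**The concern.** The patients covered by the waiver are the longest exposed in the trial, and they still take sponsor-supplied drug as trial participants. A grade 1 creatinine rise or an early transaminase rise may cause no symptoms, so collecting adverse events does not reveal it unless someone takes blood. The liver work-up in Section 10.4.2 starts from a local laboratory alert "or if the investigator notices the elevated ALT/AST/bilirubin reach the level in Section 5.2.2.1.7". Both starting points presuppose a test that the protocol no longer requires. A site that follows the text exactly keeps rules that tell it to act on laboratory values but has no scheduled occasion on which to obtain them. Detection then depends on local habit and will differ between sites.

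**Working it through.** **Step 1. Does another provision require a periodic blood test under afatinib after the lock?**

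| Provision | Survives the waiver? | Sets a periodic afatinib blood test? |
|---|---|---|
| Flow Chart laboratory row, via Section 5.2.3 | No, as written | It was the only one |
| Renal rule, Table 4.1.4.1: 1 | Yes; dose changes are still recorded | No; it acts on a value once known |
| Liver event, 5.2.2.1.7 and 10.4.2 | Yes | No; repeat testing starts after an alert |
| Diarrhoea table, 4.2.3.1: 1 (electrolyte check from grade 2) | Yes | No; symptom-led |
| Methotrexate continuation criteria, 4.1.4.2 | Yes, for methotrexate patients | Not for afatinib |
| Standard medical care, Section 8 | Yes | No test named |

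The answer is no. The required number goes from one every four weeks, plus EOT and FUV, to none. Proteinuria does not enter the loss during treatment, because urinalysis was scheduled only at screening and EOT.

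**Step 2. How many patients?** The plan gives no figure, so there is none to reproduce. Inputs:

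- 330 randomised, two thirds to afatinib (Section 7.6).
- Accrual of 9.5 per month (text of 7.6) or 12.5 per month (footnote to Table 7.6: 1). Both are used as a range. Accrual lasts A = 330/9.5 = 34.7 or 330/12.5 = 26.4 months.
- Median PFS on afatinib of 3.0 months (7.6) or 2.63 months (trial 1200.43, Section 1.2.3), with exponential times and PFS as a proxy for time on drug.
- s, the share of exits from drug for reasons other than progression. The documents give no value, so s = 0, 0.1 and 0.2 are assumptions.

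The monthly exit rate is L = (ln 2 / median)/(1 − s). With r = two thirds of the accrual rate, the expected number on afatinib 12 months after accrual ends is

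n = r × exp(−12L)/L × (1 − exp(−L·A)).

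Example with s = 0, median 3.0 and 9.5 per month: L = 0.693/3.0 = 0.231; r = 6.33; exp(−12L) = 0.0625; the last factor is 0.9997. So n = 6.33 × 0.0625/0.231 × 0.9997 = 1.71.

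**Step 3. How many four-weekly tests?** With Lw the exit rate per week (30.4375/7 = 4.348 weeks per month), the expected number of remaining four-weekly tests per patient is 1/(exp(4·Lw) − 1). In the same example 4·Lw = 4 × 0.231/4.348 = 0.2125, which gives 4.22 per patient and 1.71 × 4.22 = 7.2 over the trial.

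| s | Median (months) | n at 9.5 / 12.5 per month | Tests per patient | Tests over the trial |
|---|---|---|---|---|
| 0 | 3.0 | 1.71 / 2.25 | 4.2 | 7.2 / 9.5 |
| 0 | 2.63 | 1.02 / 1.34 | 3.6 | 3.7 / 4.9 |
| 0.1 | 3.0 | 1.13 / 1.49 | 3.8 | 4.3 / 5.6 |
| 0.1 | 2.63 | 0.64 / 0.85 | 3.2 | 2.1 / 2.7 |
| 0.2 | 3.0 | 0.69 / 0.90 | 3.3 | 2.3 / 3.0 |
| 0.2 | 2.63 | 0.37 / 0.49 | 2.8 | 1.0 / 1.4 |

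The EOT and FUV tests come on top. The chance of at least one such patient, 1 − exp(−n), is 64–89% at s = 0 and 31–77% at s = 0.1 to 0.2. A tail of long responders, which the exponential model lacks, would raise all counts.

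**The case against.** The strongest reply is that the sentence is chiefly about what must be entered in the data system, and that waived does not mean forbidden. Dose changes are still recorded, so the dose rules survive, and an investigator who must act on creatinine will presumably measure it. Safety laboratories were always local, standard care continues, and Section 3.1 even contemplates supply outside the study, with less oversight than this. Much of that stands: the intent is ambiguous rather than plainly unsafe, and symptom-led testing is untouched. But the sentence says procedures, not only data. A rule that acts on a value does not oblige anyone to obtain that value at intervals. The gap in periodic testing of patients without symptoms remains.

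Three stronger readings are tempting, and the documents do not support them.

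- *The follow-up visit is abolished, so trial completion cannot be reached.* Adverse event collection is expressly kept, and Section 5.2.2.2 runs it to the first scheduled visit after the 28-day residual effect period. That largely carries the follow-up visit with it, consistent with Sections 3.1, 6.2.3.2 and 8.6.
- *Pregnancy safeguards are lost.* The EOT test is still called mandatory in footnote 12, and the contraception, stopping and reporting rules of Section 5.2.2.2.1 are unchanged. What is missing is a sentence confirming that the test stays due.
- *Progression can no longer be detected.* Section 6.2.3.1 still requires imaging before treatment is stopped for progression. Imaging after the primary lock had already moved to local standard, with 16-weekly scans only where no standard exists. This is not a separate point.

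**Conclusion.** The point holds for laboratory monitoring under afatinib. As written, the waiver leaves no required periodic creatinine, ALT, AST or bilirubin test for patients who remain on trial drug, while the provisions that depend on those values stay in force. The size is modest: about 0.4 to 2.2 expected patients and roughly 1 to 10 on-treatment tests over the whole trial. The upper ends assume that nobody stops except at progression. The lower ends rest on an assumed 20% of other exits, for which the documents give no source. These are requirements removed, not tests shown to have been missed. A reader might infer harm to the efficacy result, but the primary PFS analysis comes before this lock and is unaffected. The status of the EOT and follow-up visits is a matter of wording only.

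**What to change.** In footnote 14 and Section 6.2.3.1, replace the blanket waiver with a named list of non-safety procedures, for example quality-of-life questionnaires, resource use, biomarker sampling and weekly visits. State that local creatinine, ALT, AST and bilirubin remain required at the four-weekly dispensing contact, which continues anyway while drug is supplied. Add one sentence confirming that the EOT visit, with pregnancy test where applicable, and the 28-day follow-up visit stay due. No new clinical rule is needed.

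The cost is about 1 to 10 local blood tests over the whole trial, the closing visits for about two patients at most, some site work after the lock, and approval of the amendment. Amendment 4 itself needed ethics committee and authority approval, so this step is real, and the change is best combined with any other pending amendment.
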